8.2. Serious Adverse Event Definition

An SAE is any AE, occurring regardless of causality, that:

- Results in death.
- Is life-threatening. Life-threatening means that, in the opinion of the Investigator or Study Sponsor, the patient/subject was at immediate risk of death from the reaction as it occurred, (i.e., it does not include a reaction that hypothetically might have caused death had it occurred in a more severe form).
- Requires inpatient hospitalization or prolongation of existing hospitalization. Hospitalization admissions and/or surgical operations scheduled to occur during the study period, but planned before the signing of the ICF, are not considered AEs if the illness or disease existed before the patient was enrolled in the trial, provided that it did not deteriorate in an unexpected manner during the trial (e.g., surgery performed earlier than planned).
- Results in persistent or significant disability/incapacity. Disability is defined as a substantial disruption of a person's ability to conduct normal life functions.
- Is a congenital anomaly/birth defect.
- Is an important medical event. An important medical event is an event that may not result in death, be life-threatening, or require hospitalization but may be considered an SAE when, based upon appropriate medical judgment, it may jeopardize the patient/subject and may require medical or surgical intervention to prevent one of the

outcomes listed in the definitions for SAEs. Examples of such medical events include allergic bronchospasm requiring intensive treatment in an emergency room or at home, blood dyscrasias or convulsions that do not result in inpatient hospitalization, or the development of drug dependency or drug abuse.

A distinction should be made between the terms "serious" and "severe" since they **are not** synonymous. The term "severe" is often used to describe the intensity (severity) of a specific event (as in mild, moderate, or severe MI; the event itself, however, may be of relatively minor medical significance (such as severe headache). This is **not** the same as "serious," which is based on patient/event outcome or action criteria usually associated with events that pose a threat to a patient's life or functioning. A severe AE does not necessarily need to be considered serious. For example, persistent nausea of several hours' duration may be considered severe nausea but not an SAE if the event does not meet the serious criteria. On the other hand, a stroke resulting in only a minor degree of disability may be considered mild but would be defined as an SAE based on the above noted serious criteria.

8.2.1. Regulatory Reporting Requirements for Serious Adverse Events

- The Investigator must notify the Sponsor of an SAE within 24 hours of the first awareness of the event.
- The Sponsor has a legal responsibility to notify both the local regulatory authority and other regulatory agencies about the safety of a study drug under clinical investigation. The Sponsor will comply with country-specific regulatory requirements relating to safety reporting to the regulatory authority, Institutional Review Board (IRB)/ Independent Ethics Committee (IEC), and Investigators.
- The Council for International Organizations of Medical Sciences (CIOMS) or MedWatch reports must be prepared for suspected unexpected serious adverse reactions (SUSARs) (Section 8.3) according to local regulatory requirements and Sponsor policy and forwarded to Investigators as necessary. The Sponsor's procedures for the reporting of SUSARs are in accordance with United States Title 21 Code of Federal Regulations (CFR)312.32 and European Union Clinical Trial Directive 2001/20/EC and the associated detailed guidance documents or national regulatory requirements in participating countries as well as IRBs/IECs where applicable.
- An Investigator who receives an Investigator safety report describing an SAE or other specific safety information (e.g., summary or listing of SAEs) from the Sponsor will review and acknowledge the report and notify the IRB/IEC, if appropriate, according to local requirements.

8.3. Suspected Unexpected Serious Adverse Reactions

A SUSAR is an event that is assessed as serious by the Investigator and/or the Sponsor that is not listed in the Reference Safety Information of the IB and has been assessed as having at least a reasonable possibility of being related to the investigational medicinal product by the Investigator and/or the Sponsor.

The Sponsor has procedures that will be followed for the recording, medical assessment, and expedited reporting of SUSARs that are consistent with global regulations, legislation, and guidance documents.

SUSARs will undergo expedited reporting to the national regulatory authorities, IRBs/IECs, and Investigators following local regulatory reporting requirements where applicable. The Sponsor is required to take the following actions:

- In the case of SUSARs with an outcome of death or that are life-threatening, the Sponsor is required to report the event within 7 days. SUSARs with any of the other outcomes are required to be reported to regulators within 15 days.
- Inform all Investigators of the SUSAR.

8.4. Adverse Events of Special Interest

Thrombotic or embolic events of any severity are AESI and should be reported as non-serious AEs or as SAEs (if appropriate) within 24 hours after the Investigator is made aware of them, as described in Section 8.8.

The Investigator will assess relationship of the AESI to and exanet as described in Section 8.5. In addition, the DSMB will periodically consider whether the occurrence of AESIs (whether related or not) warrant changes to the study (see Section 10.6.2 and the DSMB Charter).

8.5. Assessment of Causal Relationship

The Investigator should use their knowledge of the patient, the circumstances surrounding the event, and an evaluation of any potential alternative causes to determine whether or not an AE is considered to be related to the randomized treatment (andexanet or usual care). For each AE/SAE, the Investigator must document in the medical notes that they have reviewed the AE/SAE and have provided an assessment of causality.

The following categories should be used in the causality assessment of suspected adverse reactions:

Related

The AE:

- Follows a reasonable temporal sequence from the time the randomized treatment was administered; and/or
- Follows a known response pattern to the randomized treatment; and
- Does not have a likely alternative etiology.

Unrelated

The AE:

- Does not follow a reasonable temporal sequence from the time the randomized treatment was administered; and
- Was most likely produced by other factors, such as the patient's clinical state, therapeutic intervention, or concomitant therapy; or
- Was clearly and incontrovertibly due only to extraneous causes (e.g., the patient's clinical state, therapeutic intervention other than bleeding control, or concomitant therapy other than the randomized treatment) and does not meet the criteria listed above under "*Related*."

An AE with causal relationship not initially determined will require urgent follow-up to assign causality. Additionally, lack of efficacy does not necessarily constitute relatedness to the randomized therapy.

8.6. Assessment of Severity

The Investigator must determine the severity of the event according to the criteria below and the Investigator's clinical judgment. Severity describes the intensity of the AE. Events that change severity during the course of follow-up should be recorded based on their highest severity grade.

Mild Awareness of sign or symptom, but easily tolerated

Moderate Discomfort enough to cause interference with normal daily activities

Severe Inability to perform normal daily activities

8.7. Adverse Event Reporting

For all patients, the AE reporting period starts with the signing of the ICF and continues through the Day 30 Follow-up visit. For patients who have a positive anti-andexanet antibody response at the Day 30 visit, the AE reporting period will extend through their Day 120 follow-up visit.

Patients in this study who experience an andexanet-related AE or SAE will be followed until the AE or SAE is resolved or until a new stable baseline is established, even if this occurs after the Day 30 Follow-up visit. All AEs spontaneously reported by the patient and/or in response to an open question from study personnel or revealed by observation, physical examination, or other diagnostic procedures will be recorded and reported on the appropriate CRF through the Day 30 Follow-up visit.

8.8. Reporting of Serious Adverse Events and Adverse Events of Special Interest

After informed consent has been signed but prior to initiation of study treatment, only SAEs caused by a protocol-mandated intervention (e.g., invasive procedures such as biopsies, discontinuation of medications) should be reported. After initiation of study treatment, all AEs, regardless of relationship to study treatment, will be reported until 30 days after the last dose of the study treatment. After this reporting period, the Investigator is not required to actively monitor patients for AEs; however, the Sponsor should be notified if the Investigator becomes aware of any post-study SAEs that are believed to be related to prior study treatment.

All SAEs and AESIs (see Section 8.4) must be reported by the Investigator by sending the SAE Form and any pertinent source documents and recording the SAE on the AE CRF, within 24 hours from the point in time when the Investigator becomes aware of the SAE. Submission of an SAE should not be withheld even if complete information about the event is not available at the time of the initial report. Any follow-up information on a previously reported SAE or AESI should be sent promptly by the Investigator within 24 hours from the point in time when the Investigator becomes aware of it), or as requested by the Sponsor or its designee.

The Sponsor will immediately notify the Investigator about important safety or toxicology information, including neutralizing antibodies against FX or FXa identified in a patient treated with andexanet in any clinical study, as it becomes available. It is the responsibility of the Investigator to promptly notify the IRB/IEC about new and relevant safety information regarding the study drug, including serious adverse drug reactions (implied causal relationship to study treatment) involving risk to human subjects, in accordance with the applicable policies. Certain countries (e.g., the Netherlands) require the Sponsor to notify the IRB/IEC about new and relevant safety information regarding the study drug, including serious adverse drug reactions involving risk to human subjects. An unexpected event is one that is not listed by nature or severity in the Reference Safety Information.

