8.0 ADVERSE EVENT REPORTING

8.1. Adverse Event Definitions

According to the ICH guideline for GCP, an AE is any untoward medical occurrence in a clinical investigation subject administered a pharmaceutical product, regardless of causal attribution to study treatment or procedure. An AE can therefore be any unfavorable and unintended sign (including an abnormal laboratory finding), symptom, or disease temporally associated with the use of a medicinal (investigational) product, whether or not related to the medicinal (investigational) product. For the purposes of this study, a Treatment-Emergent AE (TEAE) is one that occurs at any time following treatment initiation.

Examples of AEs include:

- Any treatment emergent signs and symptoms (events that are marked by a change from the patient's baseline/entry status [e.g., an increase in severity or frequency of pre-existing abnormality or disorder or recurrence of an intermittent medical condition not present at baseline]).
- All reactions from study drug, abuse of drug, withdrawal phenomena, sensitivity or toxicity to study drug.
- Any complication or injury resulting from a study-specific procedure (e.g., thrombophlebitis from an IV line).
- Apparently unrelated illnesses.
- Injuries or accidents.
- Extensions or exacerbations of symptomatology, subjective patient-reported events, new clinically significant abnormalities in clinical laboratory, physiological testing, or physical examination.
- Abnormal laboratory findings considered by the Investigator to be clinically significant, represent a worsening from baseline, and meet any of the below-listed criteria should be reported as an AE. An abnormal laboratory value should be recorded as an AE if it:
- Is associated with clinical signs or symptoms,
- Requires an intervention,
- Results in an SAE, or
- Results in study discontinuation.

When recording an AE resulting from a laboratory abnormality, the resulting medical condition, if known, rather than the abnormality itself should be recorded (e.g., record "anemia" rather than "low hemoglobin").

When a unifying diagnosis has been made that accounts for several possible signs and/or symptoms, the unifying diagnosis should be selected as the AE term. For example, the combination of general malaise, mild fever, headache, and rhinitis should be described as "upper respiratory syndrome" if this diagnosis has been made, rather than reporting the individual symptoms as separate events.

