10.6. Safety Endpoints and Summaries

The following safety endpoints will be evaluated:

- Occurrence of TEs, confirmed by adjudication, through 30 days post-randomization.
- In-hospital mortality (during index hospitalization; all-cause, cardiovascular [CV], and bleeding).
- 30-day all-cause, CV, and bleeding mortality (the latter defined as death within 72 hours of randomization, not due to a TE).
- Proportion of patients with invasive intracranial procedures performed post-randomization to manage the intracranial hematoma and/or its complications.
- Length of initial hospitalization for primary bleeding event.
- Total time admitted to the intensive care unit during the initial hospitalization.
- Proportion of re-hospitalizations, including total number of re-hospitalizations and total days re-hospitalized, at 30 days post-randomization.
- AEs and vital signs.
- Antibodies to FX, FXa, and and exanet.
- Neutralizing antibodies to FX, FXa, and and exanet.

Safety will be assessed by examination of AEs (including central adjudication of TEs), survival status (including central adjudication of deaths), occurrence of invasive procedures, hospitalization data, laboratory parameters (i.e., antibody testing), and vital signs. Only clinically significant changes will be reported as AEs (see Section 8.1).

10.6.1. Adverse Events

Treatment-emergent adverse events (TEAEs) will be summarized by system organ class and preferred terms as defined by the Medical Dictionary for Regulatory Activities (MedDRA) with the version in effect at the time of analysis.
The number of events, the number of patients, and the percentage of patients who experienced at least one TEAE will be presented. TEAEs that are considered by the Investigator to be related to a study-related procedure; TEAEs that lead to early withdrawals; and serious TEAEs will be summarized in the same manner. Frequent TEAEs, including preferred terms with an incidence rate of \geq 5%, will also be summarized.

Concomitant medications will be coded using the World Health Organization (WHO) Drug Dictionary (DD).

10.6.2. Thrombotic Events

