⁸ For patients randomized to usual care, Investigators may initiate, within 3 hours of randomization any available therapy (including no treatment) other than and exanet to control bleeding and manage their patient during the 12-hour post-randomization period. Treatment duration will depend on usual care used.

⁹ Record blood products and hemostatic treatments used specifically for treatment of intracerebral hemorrhage.

¹⁰ Record procedures performed to evaluate bleeding source/extent and for treatment of intracerebral hemorrhage. This should include CT or MRI scans.

Protocol Amendment 3 Andexanet Alfa

¹¹ Record through initial hospital discharge and rehospitalization (as applicable).

¹² Record dates of use of anticoagulant(s) on the anticoagulant CRF.

¹³ To minimize the effects of blood pressure on hematoma expansion, Investigators should consider maintaining SBP at a target of 140 mmHg as medically warranted in both treatment arms.

¹⁴ The 12-hour and 24-hour NIHSS and GCS assessments must be performed in a blinded manner.

¹⁵ The mRS should reflect the patient's neurological status prior to acute illness (pre-morbid).

¹⁶ The Day 7 and Day 14 visits may be conducted by phone.

¹⁷ Window: Days 30-37. Patients who discontinue from the study before this visit should undergo an Early Termination visit.

¹⁸ To be performed at Early Termination only if these assessments have not yet been performed at any point during treatment.

¹⁹ Patients with a positive anti-andexanet antibody response at the Day 30 visit should return for a follow up anti-andexanet antibody test within 30 days of when the positive test is communicated to the Investigator, or approximately 120 days post-randomization, whichever is later. Only patients with a positive Day 30 anti-andexanet antibody test result are required to return for this visit. Adverse events, concomitant medications and survival status will also be collected.

²⁰ To accommodate dosing within 2 hours of the baseline scan closest to randomization, reconstitution of andexanet prior to randomization will be allowed.

²¹ Adverse events including SAEs and TEs, and survival will be followed through the Day 30 post-treatment visit for all patients.

²² TFPI activity measurements will be included for plasma samples collected for anti-fXa activity (baseline [-15min to -1min], 1h, and 2h), thrombin generation (12h) and neutralizing antibodies FX/FXa (30d).

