- For start date: If the day is missing, then impute with 01, and if both the day and the month are missing, then impute with 01-Jan.
- For end date: If the day is missing, then impute with the last day of that month, and if both the day and the month are missing, then impute with the last visit/contact/survival/death day of study or Day 30.
- If the year is missing, then keep as is. No imputation is required if the complete date is missing.

Definition of Baseline Values

Baseline is defined as the most recent nonmissing assessment within the protocol-defined visit window prior to randomization. If there is no assessment within the visit window of randomization, then the assessment closest to randomization prior to treatment will be used as baseline. Data that are outside the baseline assessment windows specified above will not be excluded from analyses but will be identified as protocol deviations.

Start of Study Treatment

For and exampt treatment group, the start of study treatment will be the start of and exampt. For the UC treatment group, the start of study treatment will be the start of the specific UC drug received by the participant, or if the UC consists of no treatment, then the start of study treatment will be the randomization date for the participant.

Restart of Anticoagulants

The time when anticoagulants were restarted is defined as (date restart anticoagulation - date of the first study treatment) + 1. If the participant is assigned to UC and receive no treatment, then the date of the first study treatment will be replaced by the date of randomization. Oral anticoagulants will be summarized separately.

Study Day

For participants who are randomized to UC group and received no treatment, the study day is calculated based on randomization date. For events prior to randomization, the study day is calculated as date of event - date of randomization; for events on or after randomization, the study day is calculated as date of event - date of randomization + 1. For other participants, the study day is calculated based on the date of treatment initiation, using the same formula as above. Study day is referred as "day" in outputs.

Calculation of On Treatment Nadir

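### Protocol 8.7 and 8.8 conflict on when AE collection starts and ends, and the TEAE start is arm-dependent, leaving up to 150 minutes' difference in uncounted time after randomization

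*Protocol*

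**What the plan says.** **Collection.** Protocol 8.7: "For all patients, the AE reporting period starts with the signing of the ICF and continues through the Day 30 Follow-up visit". Protocol 8.8, first paragraph: "After informed consent has been signed but prior to initiation of study treatment, only SAEs caused by a protocol-mandated intervention" should be reported; then "After initiation of study treatment, all AEs, regardless of relationship to study treatment, will be reported until 30 days after the last dose". The second paragraph of 8.8 requires all SAEs and AESIs to be sent within 24 hours of awareness and names no start time. Protocol 8.4 makes thrombotic events (TEs) of any severity AESIs and refers to 8.8 for how to report them. Appendix A marks AE recording from the screening column onward.

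**Counting.** Protocol 8.1: "a Treatment-Emergent AE (TEAE) is one that occurs at any time following treatment initiation". SAP 5.7.2 uses the same definition. SAP 6.1 then fixes the start of treatment. For andexanet it is the start of andexanet. For usual care: "For the UC treatment group, the start of study treatment will be the start of the specific UC drug received by the participant". If usual care is no treatment, it is the randomization date. SAP Table 2 keeps untreated usual-care patients in the Safety Set.

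**Timing of treatment.** Protocol 3.1 and 6.2 ask for andexanet to start no later than 30 minutes after randomization. For usual care, Appendix A footnote 8 states: "Investigators may initiate, within 3 hours of randomization any available therapy (including no treatment").

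**Endpoints.** Protocol 10.6 lists "Occurrence of TEs, confirmed by adjudication, through 30 days post-randomization". SAP 5.7.2.5 times 30-day deaths and bleeding deaths from randomization.

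**The concern.** In an open-label comparison, AEs should be collected and counted from the same moment in both arms, and that moment should not depend on anything decided after randomization. Two features of the plan depart from this.

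First, a site cannot follow both 8.7 and 8.8 between consent and first treatment. A site that follows the first paragraph of 8.8 leaves out most events in that interval, and the part of it that falls after randomization can be longer when the assigned treatment is a usual-care drug. For usual care with no treatment, the interval in 8.8 never closes and there is no last dose to end reporting.

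Second, treatment-emergence starts at a point that differs by arm. Within usual care it also depends on whether the treating physician later gives a drug, which may itself reflect the patient's early course.

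At stake are the general AE and SAE tables in the first hours and, through collection, the completeness of TE ascertainment. SAP 1.2 and 6.1 describe the adjudication committee as working from reported AEs. The sponsor's additional search for TEs (Protocol 7.6 and 10.6.2) is also a review of AEs. An event never entered would be visible to neither.

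**Working it through.** The plan states no figure on this point, so there is none to reproduce. The check compares the definitions and does the window arithmetic.

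**Step 1: the two collection rules.**

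| | Protocol 8.7 | Protocol 8.8, first paragraph |
|---|---|---|
| Start of full AE reporting | Consent, all patients | Initiation of study treatment |
| Before that start | Not applicable | Only SAEs from a protocol-mandated intervention |
| End | Day 30 visit (Day 120 if antibody-positive) | 30 days after last dose |
| Usual care, no treatment | Defined | No start, no end |

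The rules differ at both ends. If dosing is on Day 1, 30 days after the last dose is Day 31 (1 + 30), whereas Appendix A lets the Day 30 visit fall on Days 30 to 37.

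**Step 2: maximum time after randomization before an event is treatment-emergent** (SAP 6.1 start with the Protocol 3.1 and Appendix A windows).

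- Andexanet: 30 min
- Usual care with a drug: 3 × 60 = 180 min
- Usual care, no treatment: 0 min

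**Step 3: differences.**

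- Drug-treated usual care minus andexanet: 180 − 30 = 150 min (2.5 h)
- Andexanet minus untreated usual care: 30 − 0 = 30 min, in the opposite direction
- Within usual care, drug-treated minus untreated: 180 − 0 = 180 min

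**Step 4: the 150 min as a share of follow-up.**

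- First 12 h: 150 / 720 = 20.8%
- First 24 h: 150 / 1,440 = 10.4%
- 30 days: 150 / 43,200 = 0.35%

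**Step 5: illustrative ceiling on uncounted events.** The documents give no AE timing. Assume a fraction f of 30-day AEs falls in the first 24 h, spread evenly within it, and every patient starts at the latest allowed time. The extra share of AEs not counted in drug-treated usual care, relative to andexanet, is f × 150 / 1,440.

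- f = 1/30 (even over 30 days): 0.35%
- f = 0.10: 1.0%
- f = 0.20: 2.1%
- f = 0.30: 3.1%

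**Step 6: one event under three starts.** Take an AE with a recorded onset 60 min after randomization. With andexanet started at 30 min it is treatment-emergent. With a usual-care drug started at 120 min it is not. With usual care and no treatment it is. The two usual-care patients differ only in what was given later.

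**Step 7: after the change.** With randomization as the common start, the uncounted window is 0 min in all three groups and the 150 min difference becomes 0.

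**The case against.** The best defence is that most of the plan points to collection from consent: 8.7 says so for all patients, Protocol 3.3 starts data collection at consent, and Appendix A records AEs from screening. On that reading 8.8 is a drafting slip. This is a fair reading, but the plan does not say which section governs, and 8.8 is where 8.4 sends sites for TEs.

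On size, 150 min is an outer limit. Protocol 3.1 intends treatment as soon as possible in both arms, and the 30 min for andexanet is a target: the SAP per-protocol rules foresee later starts, which would narrow the gap. Hematoma expansion and related deterioration in the first 12 h are generally not AEs in either arm (Protocol 8.1.1), and an AE on the first-dose day with no recorded time counts as treatment-emergent (SAP 6.1). All of this stands and makes the effect smaller. Treatment-emergence from first dose is also a stated and common definition; the difficulty is using it as the only comparative window when the start differs by arm.

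Three stronger readings are tempting but unsupported:

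- *Events in untreated usual care are never counted.* SAP 6.1 counts them from randomization and Table 2 keeps these patients in the Safety Set. Only the site rule in 8.8 lacks a start and an end for them.
- *The bias runs one way.* Untreated usual care opens earlier than andexanet and drug-treated usual care can open later. The mix and the actual start times are not given.
- *The TE and mortality comparisons are miscounted.* Both are timed from randomization, and SAP 5.7.2.6 summarizes adjudicated TEs without a treatment-emergence filter. The second paragraph of 8.8 also requires every AESI to be reported. For TEs, what remains is the chance that a site acts on the first paragraph and does not enter the event.

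**Conclusion.** The concern holds as a contradiction between Protocol 8.7 and 8.8, a gap in 8.8 for untreated usual care, and an unequal start for the general TEAE tables. The inequality is at most 150 min between andexanet and drug-treated usual care if both treatments start at their planned limits. That is a sizeable part of the first 12 h and very little of 30 days. The 0.35% to 3.1% range rests on assumed event timing and latest-possible starts for everyone, so actual starts would normally put it lower. Neither the net direction nor the number of events can be derived from the documents. A reader might also infer that the DSMB is shown incomplete safety data; the documents support this only as a possibility at sites that apply the first paragraph of 8.8. It should be corrected, because the inconsistency is avoidable and uncollected events cannot be recovered at analysis, but it does not undermine the TE or mortality endpoints as defined.

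**What to change.** 1. **Protocol 8.8:** align with 8.7. Collect all AEs, SAEs and TEs from randomization at the latest through the Day 30 visit in both arms, keeping the Day 120 extension in 8.7. Let any restriction to procedure-related SAEs apply only before randomization. This also gives untreated usual care a start and an end.
2. **SAP 5.7.2 and 6.1:** base the comparative AE and SAE summaries on onset at or after randomization in both arms. Add a flag for events before first treatment, and keep the TEAE summary from first treatment as supportive.
3. **Protocol 8.1:** state that the TEAE definition serves the supportive summary.

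The cost is wording in three places, one derived flag and one extra set of tables. The downside is that a few pre-dose events that cannot be due to the drug enter the main comparison; the flag identifies them.
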